10 STUDY SELECTION CRITERIA

10.1 INCLUSION CRITERIA

For inclusion in this study, subjects must meet all of the following criteria:

1. Previously enrolled in the TearCare arm of the TearCare Pilot Study (protocol number 05429)
2. Reports dry eye symptoms within 3 months of the baseline examination with a Standard Patient Evaluation for Dryness (SPEED) score ≥ 6
3. TBUT of <10 seconds in at least one eye
4. Willing to comply with the study, procedures, and follow-up
5. Willing and able to provide consent

10.2 EXCLUSION CRITERIA

A subject who meets any of the criteria listed below will be excluded from the study:

1. Any active ocular or peri-ocular infection or inflammation
2. Recurrent eye inflammation within the past 3 months
3. Ocular surgery, oculoplastic surgery, ocular injury, Ocular Herpes Simplex, or Herpes Zoster
4. Ocular surface abnormalities that may affect tear film distribution or treatment
5. Abnormal eyelid function in either eye
6. Diminished or abnormal facial, periocular, ocular or corneal sensation
7. Ocular surface abnormalities such as corneal epithelial defects, ulcers, corneal dystrophies
8. Systemic diseases resulting in dry eye (e.g. Sjogren's syndrome)
9. Allergies to silicone tissue adhesives
10. An absence or fibrosis of the Meibomian glands (e.g. ectodermal dysplasia).
11. Unwillingness to abstain for the duration of the study from systemic medication known to cause ocular dryness (e.g. Accutane, antihistamines, etc.)

- 12. Anyone who requires chronic use (i.e. for any portion of the study) of topical ophthalmic antibiotics, steroids, non-steroidal anti-inflammatory medications or who has been on any of these medications within the past 30 days.
- 13. Participation in another ophthalmic clinical trial within the past 30 days
- 14. Co-existing conditions that could interfere with the assessment of safety or efficacy of treatment (e.g. macular disease, pregnancy, nursing, etc.)

11 STUDY PROCEDURES

11.2 NUMBER OF SUBJECTS AND STUDY DURATION

Up to 12 subjects will be enrolled in the study. Each subject will receive one in-office TearCare procedure and then will be followed for 6 months. It is anticipated that enrollment in the study will take 1-2 months. Including the 6-month follow-up period, the study is expected to last 7-8 months.

11.3 MATERIAL AND EQUIPMENT

11.4 INFORMED CONSENT AND POINT OF ENROLLMENT

The IRB-approved informed consent will be presented and explained to each prospective subject by the investigator or a trained clinical professional. Once the subject has had ample time to read the consent form, has been informed of all aspects of the study, and has had an opportunity to ask questions, the subject will be given a choice to voluntarily confirm his or her participation in the study as documented by completion of the Informed Consent. After signing the Informed Consent and the HIPAA (Health Insurance Portability and Accountability Act) authorization, the subject can then proceed with the baseline visit. The subject has the right to withdraw from the study at any time without consequences, as indicated in the Informed Consent Document.

The subject's signed and dated informed consent must be obtained before conducting any procedure specifically for the study. Subjects are enrolled upon signing the ICD even if they subsequently fail to meet the eligibility criteria.

The principal investigator(s) must retain the original, signed written Informed Consent Document. A copy of the written Informed Consent Document must be given to the subject.

11.5 BASELINE VISIT

11.5.1 SCHEDULING THE BASELINE VISIT

Since dry eye drops and lubricants can affect the endpoint assessments, instruct subjects not to use any of these products within 2 hours of the Baseline visit.

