8 STUDY ENDPOINTS

8.1 EFFECTIVENESS ENDPOINTS

[figure not shown]
The primary effectiveness endpoint of the study is the change from baseline to 4 weeks in Tear Break-Up Time (TBUT).

Secondary effectiveness endpoints include the change from baseline to follow-up in the following:

- **Meibomian Gland Assessment**²⁸ scores for the following:
 - The number of Meibomian glands yielding clear liquid secretions (grade 3)
 - The number of glands secreting any liquid (clear or cloudy with grade 2 or 3)
 - The total Meibomian Gland Score
- **Dry Eye Symptoms and Quality of Life**, as measured by:
 - The Standard Patient Evaluation of Dry Eye (SPEED) II questionnaire²⁹, which measures the severity and frequency of dry eye symptoms
 - Ocular Surface Disease Index (OSDI) Questionnaire³⁰. The OSDI consists of 12 questions to assess ocular symptoms (the Ocular Symptoms subscale), their impact on patient vision-related functioning (Vision Related Function subscale), and environmental factors triggering the symptoms (Environmental Triggers subscale).
 - Symptom Assessment in Dry Eye (SANDE) Questionnaire.^{31, 32} The SANDE is a 2-question survey which uses a visual analog scale to assess the frequency and severity of dry eye symptoms
- Corneal & conjunctival staining scores

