9 STUDY DESIGN

This is a prospective, non-randomized, single-center case series study. No specific attempts will be made for minimization of bias, such as blinding or masking.

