11.5.4 MANAGEMENT OF DRY EYE SYMPTOMS DURING FOLLOW-UP

During follow-up, if subjects require relief of their dry eye symptoms, they should only use the same type of drops or lubricants they used prior to the start of the study. Subjects should record their daily use of lubricants on the Lubricant Drop log.

Subjects **should not** use any other method of relieving dry eye symptoms, including any of the following:

- Warm compress
- Restasis or Xiidra
- Other dry eye treatments (e.g. Lipiflow, TrueTear, iLux, punctal plugs, etc.)

NOTE: If a subject had a punctal plug at the baseline visit and it falls out during the study, it should be replaced.

Review these instructions with subjects at the end of the Baseline visit and provide them with the Lubricant Drop log. They should complete the log each day and bring it back to the clinic at each follow-up visit.

[figure not shown]

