11.6 FOLLOW-UP VISITS

Prior to the Visit: Reminder Call

Since dry eye drops and lubricants can affect the endpoint assessments, it is important to call subjects a few days before their follow-up visits to remind them that on the day of the Follow-up visit, they should not to use any of these products before the Follow-up visit.

Order of Procedures During the Follow-Up Visit

Follow-up exams should not be performed by the clinician who performed the TearCare procedure.

A large block of text is completely redacted with black bars, representing a list of procedures or steps.

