14 STATISTICAL CONSIDERATIONS

14.1 HYPOTHESIS

This pilot study is not a hypothesis-driven study.

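### Eye drops and lubricants are barred for 2 hours before Baseline but for the whole visit day up to each Follow-up visit, and the two rules are not reconciled

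*Combined protocol and SAP*

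**What the plan says.** For Baseline, section 11.5.1 asks the site to "instruct subjects not to use any of these products within 2 hours of the Baseline visit". The products are dry eye drops and lubricants.

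For later visits, section 11.6 introduces a reminder call: "Since dry eye drops and lubricants can affect the endpoint assessments, it is important to call subjects" a few days ahead. Subjects are told that "on the day of the Follow-up visit, they should not to use any of these products before the Follow-up visit".

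Between visits, section 11.5.4 lets subjects use the type of drop or lubricant they used before the study and record it daily. It sets no abstention period before a visit. On the recording form it says: "Review these instructions with subjects at the end of the Baseline visit and provide them with the Lubricant Drop log". The TBUT method in Appendix A (24.3) sets no abstention period either.

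Section 8.1 defines the primary endpoint as the change in TBUT from baseline to 4 weeks. The secondary effectiveness endpoints are also changes from baseline. On design, section 9 states: "This is a prospective, non-randomized, single-center case series study".

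**The concern.** A change from baseline is interpretable only if both measurements are taken under like conditions. The protocol itself names recent drop use as something that can alter the measurements, and it sets out to control it, but it sets a different limit at each end of the contrast.

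In a randomized comparison, a difference in conditions between baseline and follow-up would apply to both arms and would largely cancel. Here there is no concurrent arm, so any shift it causes stays in the estimated change and cannot be separated from the effect of re-treatment. Baseline TBUT also decides entry (below 10 seconds in at least one eye, section 10.1), so drop exposure at that visit could bear on eligibility as well as on the baseline value.

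**Working it through.** The plan gives no figure to reproduce here. The check is a comparison of the two rules, followed by what they imply for the change score.

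**Step 1. Apply both rules to the same drop use** (drop times are illustrative).

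| Last drop before the visit | Baseline (11.5.1) | Follow-up (11.6) |
|---|---|---|
| Same day, 1 h before | barred | barred |
| Same day, 3 h before | allowed | barred |
| Evening before | allowed | allowed |

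Only the middle row is treated differently. Subjects who use no drops, or none on the day of Baseline, are unaffected.

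**Step 2. Compare the minimum drop-free intervals.** At Baseline the minimum is 2 h. At Follow-up it runs from the start of the visit day to the visit. Visit times are not in the documents. Assuming visits between 08:00 and 17:00, and a day that starts at midnight:

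- 08:00 visit: 2 h against 8 h. The rules differ for drops used between midnight and 06:00.
- 17:00 visit: 2 h against 17 h. The rules differ for drops used between midnight and 15:00.

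These are permitted minimums, not likely intervals. For early visits the practical difference is small; for afternoon visits it covers most of the waking day. If the last drop before a Follow-up visit was taken the evening before, the interval also includes the night.

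**Step 3. Carry this into the endpoint.** Let r_B and r_F be the mean residual effect of recent drops on TBUT at Baseline and at Follow-up. Then

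observed mean change = true mean change + (r_F − r_B).

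Suppose k of 12 subjects used a drop in the differing window at Baseline, each with residual effect d, and complied at Follow-up with no residual effect. The shift is then −(k/12) × d. The documents give neither k nor d, nor the sign of d, nor how long a drop acts. If k or d is zero, the shift is zero.

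**Step 4. A yardstick, not an estimate.** Section 7.2 reports a pilot TearCare change at 1 month of 11.7 seconds with SD 2.6. If that SD applies here with one value per subject and n = 12, the standard error of the mean change is 2.6/√12 = 0.75 s. For the shift to equal one standard error, |d| would have to be 0.75 × 12/k:

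- k = 12: 0.75 s
- k = 6: 1.5 s
- k = 3: 3.0 s

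A shift of 0.75 s would be 0.75/11.7 = 6.4% of the pilot change. Nothing in the documents says whether effects of this size occur.

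**Step 5. Look for a safeguard.** The Lubricant Drop log is issued at the end of Baseline, so it cannot show drop timing before that visit. The CRF is not visible, so recording of the last drop elsewhere cannot be excluded.

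**The case against.** The strongest reply is that the rules do not conflict operationally. They govern different visits, and staff can follow both. At any clinic hour after 02:00, a subject who meets the Follow-up rule has also gone at least 2 hours without drops, so every visit shares a 2-hour floor. If a drop's effect is gone by then, the longer rule changes nothing. This stands as far as it goes: the documents do not show that 2 hours is too short. Nor do they show that it is long enough, and the sponsor imposed a longer restriction at Follow-up for the same stated reason.

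The second reply is that little depends on the answer. Section 14.1 states: "This pilot study is not a hypothesis-driven study". Section 14.3 sets no pass/fail criteria, section 14.4 limits the analysis to basic descriptive statistics, and section 9 disclaims specific efforts to minimize bias. This also stands, and it limits the weight of the point. But the mean change is what a descriptive study reports, section 22 provides for publication, and sections 11.5.1 and 11.6 show that the sponsor did mean to control drop use.

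The third reply is that some text cannot be seen. Part of section 11.6 is redacted, and sections 11.1 and 11.5.3 are not in the public text. An explanation or a last-drop check could sit there. That limits any claim that the plan lacks a safeguard. It does not alter two visible instructions that are complete as written and differ.

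**Conclusion.** The concern holds as a minor point. The visible text sets two different abstention rules for the two ends of a within-subject change, gives one reason for both, and does not reconcile them. Confidence in that reading is high.

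No size or direction of bias is claimed. Any effect requires that some subjects use drops on the day of Baseline more than 2 hours before the visit, and that those drops still influence the assessments at the visit. The documents settle neither condition. With "Up to 12 subjects will be enrolled in the study" in section 11.2 and no decision rule, the consequence is confined to how cleanly the reported change can be read.

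**What to change.** Before the first Baseline visit, reconcile sections 11.5.1 and 11.6 so that one identically worded abstention rule applies at Baseline and at every Follow-up visit. Which rule to adopt is for the sponsor; this review does not propose one. If the sponsor has a reason for keeping the rules different, the protocol should state it.

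If the CRF does not already do so, record the time of the last drop or lubricant at each visit, including Baseline. The drop-free intervals could then be reported alongside the TBUT changes.

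The cost is a short wording change and at most one CRF field, with no added visits, staff or subjects. If the Baseline wording is changed, two points need weighing: the instruction reaches people who have not yet signed consent (section 11.4), and eligibility, including the TBUT criterion, is confirmed at that same visit (sections 10.1 and 11.5.2).

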11.5.2 BASELINE EXAMS AND QUESTIONNAIRES

After the subject has signed the informed consent form and agreed to participate in the study, the exams, tests and questionnaires listed in the Baseline column of Table 2 should be performed. Refer to Appendix A for instructions for performing the exams and administering the questionnaire.

If, at any point during the visit the subject fails to meet a subject selection criterion, then the visit can be terminated. Subjects who fail to meet all the selection criteria will be considered a screen failure and will be withdrawn from the study. Screen failures will not count toward the total enrolled and treated number of subjects.

After all required measurements have been obtained and it has been confirmed that the subject meets all the Subject Selection Criteria, then the subject will receive the TearCare procedure.

11.5.4 MANAGEMENT OF DRY EYE SYMPTOMS DURING FOLLOW-UP

During follow-up, if subjects require relief of their dry eye symptoms, they should only use the same type of drops or lubricants they used prior to the start of the study. Subjects should record their daily use of lubricants on the Lubricant Drop log.

Subjects **should not** use any other method of relieving dry eye symptoms, including any of the following:

- Warm compress
- Restasis or Xiidra
- Other dry eye treatments (e.g. Lipiflow, TrueTear, iLux, punctal plugs, etc.)

NOTE: If a subject had a punctal plug at the baseline visit and it falls out during the study, it should be replaced.

Review these instructions with subjects at the end of the Baseline visit and provide them with the Lubricant Drop log. They should complete the log each day and bring it back to the clinic at each follow-up visit.

[figure not shown]

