13.4 RISKS ASSOCIATED WITH PARTICIPATION IN THE CLINICAL INVESTIGATION

As with any type of eye procedure, there are potential risks that are associated participating in the investigation including:

- Post-procedure Discomfort
- Blurred Vision
- Inflammation of eyelids

In addition, subjects who are asked to discontinue pre-procedure dry eye medications may note that their eyes feel drier. All anticipated study risks are listed in Section 12.2.

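### Does barring other dry eye therapies only from the end of the Baseline visit distort the change in tear break-up time?

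*Combined protocol and SAP*

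**What the plan says.** The primary endpoint (section 8.1) is the within-subject change in TBUT from baseline to 4 weeks. There is one uncontrolled group of up to 12 subjects, all from the TearCare arm of the pilot (sections 9, 11.2 and 14.2).

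Section 11.5.4 governs dry eye therapy during follow-up:
- Lubricants continue: "they should only use the same type of drops or lubricants they used prior to the start of the study".
- Existing plugs are kept: "If a subject had a punctal plug at the baseline visit and it falls out during the study, it should be replaced".
- Otherwise subjects should not "use any other method of relieving dry eye symptoms, including any of the following". The list names warm compresses, Restasis or Xiidra, and other dry eye treatments.
- On timing, the site is told: "Review these instructions with subjects at the end of the Baseline visit".

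By then the baseline data exist, because section 11.5.2 places the procedure at this point: "After all required measurements have been obtained and it has been confirmed that the subject meets all the Subject Selection Criteria".

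Before baseline, section 11.5.1 deals with drops and lubricants and says to "instruct subjects not to use any of these products within 2 hours of the Baseline visit". Exclusion criterion 12 in section 10.2 covers anyone needing chronic use of "topical ophthalmic antibiotics, steroids, non-steroidal anti-inflammatory medications or who has been on any of these medications within the past 30 days". Section 13.4 adds that "subjects who are asked to discontinue pre-procedure dry eye medications may note that their eyes feel drier", without saying when they are asked.

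**The concern.** Lubricants and existing plugs are carried across baseline unchanged. The remaining therapies in 11.5.4 are only barred, and only from a point after baseline TBUT has been recorded. A subject who uses compresses or Restasis up to the visit and then stops has a baseline on therapy and a 4-week value off it. With no control group, that subject's change cannot be split into a part due to stopping and a part due to re-treatment.

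Prior use is plausible. Subjects were treated over a year before this study and followed in the pilot for 6 months, so more than 6 months passed outside any study rule. Section 5 describes compresses as a very common prescription. The protocol also accepts in section 11.5.1 that topical products can influence the assessments, and section 13.4 expects some subjects to stop medication. At stake is how the mean TBUT change is read as an effect of re-treatment.

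**Working it through.** **1. Which therapies could change status across baseline (readable text)**

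| Therapy | Before baseline | After baseline | Status can change? |
|---|---|---|---|
| Drops, lubricants | 2-hour rule (11.5.1) | same type continues | not withdrawn |
| Plug already in place | no rule | replaced if lost | not withdrawn |
| Warm compresses | no rule | barred | yes |
| Restasis, Xiidra | criterion 12, if read to include them | barred | yes, unless criterion 12 applies |
| Other treatments listed | no rule | barred | yes, if in ongoing use |

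A procedure completed before baseline cannot be withdrawn by a later bar. Any lasting effect of it is carry-over, which is a separate matter.

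**2. Direction**

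Stopping a therapy that raised TBUT lowers the 4-week value, so the gain is understated. Stopping one that had no effect causes no bias. Overstatement needs a therapy that was lowering TBUT. Section 13.4 leans towards understatement, but it speaks of how eyes feel, not of TBUT.

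**3. Inputs**

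From section 7.2: TearCare arm change 11.7 s (SD 2.6), compress arm change -0.3 s (SD 1.1), 24 subjects in total. From section 14.2: 12 in the TearCare arm, so 24 - 12 = 12 in the compress arm. The sample size of 12 is a head count with no power calculation to reproduce. The pilot comparison does reproduce: Welch t = (11.7 + 0.3) / sqrt(2.6²/12 + 1.1²/12) = 12.0/0.815 = 14.7, p = 3 × 10⁻¹⁰, consistent with the stated p < 0.0001.

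**4. Compresses**

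If k of 12 subjects stop and each shifts by w seconds, the mean moves by k × w / 12.

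- 95% interval for the compress arm, t(0.975, 11) = 2.201: -0.3 ± 2.201 × 1.1/√12 = -0.3 ± 0.70, or -1.0 to +0.4 s.
- Assumption: stopping reverses that before-after change, which is itself uncontrolled.
- All 12 stop: 0.3 s overstated (0.3/11.7 = 2.6%). The range runs from 1.0 s overstated (8.5%) to 0.4 s understated (3.4%).
- One stops: from 0.08 s overstated (0.7%) to 0.03 s understated (0.3%).

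For scale, the 95% half-width of the mean TearCare change, if the pilot SD recurs with n = 12, is 2.201 × 2.6/√12 = 1.65 s. This exceeds either compress bound.

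**5. Other barred therapies**

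The documents give neither the number of users nor an effect, so k and w below are assumptions.

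| Subjects stopping | Shift in mean for w = 1 to 5 s | Share of 11.7 s |
|---|---|---|
| 1 | 0.08 to 0.42 s | 0.7 to 3.6% |
| 3 | 0.25 to 1.25 s | 2.1 to 10.7% |
| 6 | 0.50 to 2.50 s | 4.3 to 21.4% |

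A 10% shift needs 0.1 × 11.7 × 12 = 14.0 subject-seconds, for example 7 subjects at 2 s each. Matching the sampling half-width needs 1.65 × 12 = 19.8. In the largest cell, a gain of 11.7 s would correspond to 11.7 - 2.5 = 9.2 s or 11.7 + 2.5 = 14.2 s once the shift is removed. The description of a large rise in TBUT survives both.

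**The case for a change.** The best argument for a change is that it costs little: one sentence on timing, one line on the case report form and one flagged listing, with nobody lost from a closed pool of 12. Last-use dates not taken at baseline may be hard to recover. A small shift is supported by document data for compresses only. For Restasis, Xiidra and the other treatments it is a judgement, and without a record of use no reader could test it.

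Three parts of this stand. The visible text does leave the timing open, the size for the other therapies is unknown, and nothing in a single-group design separates withdrawal from re-treatment.

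The step to a required change does not. Section 11.5.2 sends the content of the baseline visit to Table 2. That table, with sections 11.1 and 11.5.3, cannot be read in the public copy, and part of 11.6 is redacted. A therapy history or a timing rule would naturally sit there. Section 20.3.3 already requires records of each subject's condition on entry and relevant medical history, though it names no last-use date. Section 5 also reports that compresses have been poorly accepted by patients, which weakens the case for widespread use. Although section 9 disclaims any particular effort against bias, section 11.6 keeps the treating clinician away from the follow-up exams. That does not address withdrawal, but the study is not without safeguards.

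**Conclusion.** No change to the plan is needed. The sequence is as described: in the readable text the bar begins after baseline TBUT is measured, and no section expressly sets a rule for the barred therapies before that. Sections 11.5.4 and 13.4 do not contradict each other; neither dates the discontinuation, and when it falls is for the sponsor to state.

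The effect is conditional on use that nothing in the documents shows. For compresses it is 0.3 s if all 12 stop, and at most 1.0 s, against 11.7 s. This rests on the pilot compress arm being a fair guide and on stopping reversing its change. For the other therapies no size can be given. It would matter only if several of the 12 stopped a therapy with a strong effect on TBUT, and if that therapy had been helping, the re-treatment gain would be understated.

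Sections 14.1, 14.3 and 14.4 set no hypothesis, no pass/fail rule and descriptive statistics only, so no decision turns on a shift of this kind. With at most 12 subjects, an analyst who finds a stopped therapy in the records can mark that subject when describing the results. This is a gap in detail that sensible conduct and reporting fill.
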